## 8 Analysis of other secondary outcome definitions and analysis plan

### 8.1 Treatment initiation

Treatment initiation status will be declared “yes” if a participant had intake of at least one dose of the medication after randomization, and “no” otherwise. By this definition, there will be no undetermined treatment initiation status, and all mITT and PP sample will have treatment initiation. Therefore, the analytic sample for the treatment initiation will be the ITT sample only.

### 8.2 Treatment initiation hypothesis

A higher proportion of patients in the PN arm will initiate treatment compared to the DOT arm.

#### 8.2.1 Statistical Model

All statistical procedures and models applied to the analysis of SVR detailed above will also be applied except for the missing data imputation which is unnecessary. By the definition of treatment initiation, only ITT sample will be analyzed.

#### 8.2.2 Power analysis

We hypothesize that a higher proportion of patients in the PN arm will initiate treatment compared to the DOT arm, which is expected to have 60% treatment initiation rate. With the planned N=1000 ITT sample size, we will be able to detect a minimum of 12% difference (i.e., 60% vs. 72%, OR=0.58) in any outcome in a multivariable logistic regression model in which confounding variables will explain 10% of variation in the predictor variable.

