## 11.4 Sample Size Determination

Sample size N=300 per arm, or a total of N=600, was determined based on feasibility of recruitment from all sites during the study period. Power analysis for each hypothesis below is conservatively conducted based on a reduced sample size (N= 270 per arm, or N=540 in total) after considering 10% attrition rates. The target power is 80% with a two-sided significance level of 0.05. To this end, minimally detectable effect sizes and widths of 95% confidence intervals were computed with those parameters and the sample size after attrition.

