### **Power analysis: Minimally detectable effect sizes**

**SVR:** Considering the base 80% SVR rate of in PN arm, a minimum of 9% difference between the two arms will be detected (i.e., 89% vs. 80%, Odds Ratio (OR)=2.1) in a multivariable logistic regression model in which confounding variables will explain 10% of variation in the predictor variable. This study posits that a >9% difference in SVR between the PN and mDOT groups will be clinically significant based on studies that showed that SVR in treatment naive patients was >90% [14].

Mixed effects logistic regression models for the undetectable HCV load will be able to detect even smaller percent point difference since they will utilize repeated measures for each subject no matter how large within-subject outcome correlations will be.

**Treatment initiation rate:** With anticipated 60% treatment initiation rate in the mDOT arm, a minimum of 7% difference will be detectable (i.e., 60% vs. 67%, OR=0.74) in any outcome in a multivariable logistic regression model in which confounding variables will explain 10% of variation in the predictor variable. Note that sample size for this analysis will be N=1000, the total number of randomized participants.

**Adherence rate:** With expected 80% adherence rate in the PN arm, a minimum of 9% difference in adherence rates between the 2 arms will be detectable (i.e., 89% vs. 80%, OR=2.1) in a multivariable logistic regression model. Per the repeatedly measured continuous adherence percentage outcome, mixed effects linear models will be able to detect standardized effect sizes (mean difference divided by a pooled Standard

Deviation (SD)) greater than 0.2 irrespective of magnitudes of within-subject outcome correlations over time. In a previous DOT study, a standardized effect size of mDOT vs. TAU was estimated to be 0.6.

**Treatment completion rate.** Under the expected 80% completion rate in the PN arm, a minimum of 9% difference in completion rates between the two arms will be detectable (i.e., 89% (mDOT) vs. 80% (PN), OR=2.1).

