### 3.3 Per protocol analytic sample

This per protocol (PP) analytic sample includes the enrolled study participants who 1) were randomized; 2) initiated treatment; 3) complied with the randomly assigned models of care without cross over any time during the 12-week treatment; and 4) had SVR outcome data (yes vs. no). This sample is referred to as the per-protocol (PP) analytic sample. The PP sample will be a subset of the mITT sample which is in turn a subset of the ITT sample.

The intention-to-treat principle reflects the principle that once the intervention was randomly assigned to a participant, the participant's intervention assignment will not change in the analysis even if s/he crossed over the other intervention during the trial period or did not complete intervention activities. The application of this ITT principle reflects the real-world goal of the HERO study which is to treat all PWID with HCV (i.e., all randomized individuals).

However, as the HERO study was designed as of a pragmatic randomized clinical trial (RCT), the ITT sample will not be used as the primary analytic sample because the outcomes are defined conditions on the initiation. Furthermore, the primary (SVR) and several of the other secondary outcomes (treatment completion, adherence) are only relevant among those who initiated treatment.

**All statistical analyses proposed in the present SAP will be repeated for each analytic sample.** Comparison across the three analytic samples will be compared to assess internal or external validities or limitations of the study findings. In particular, analysis of the secondary ITT sample will provide estimates of milestones along the HCV cascade of care by study arm and in the full sample. All statistical analyses will be conducted using SAS v9.4 and R 3.5 or higher, and a two-tailed significance level of 0.05 will be applied to all testing and confidence intervals.

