Review of the monthly enrollment reports during the conduct of the study, however, consistently revealed that few participants have cirrhosis to the extent that there are sites and clinics without any randomized participants with cirrhosis. This imbalance raises a concern with respect to the logistic model fitting which may not result in convergence in regression coefficient estimation algorithms due to a potentially ill-conditioned data matrix. If this occurs, we plan to

remove the cirrhosis term in the above model and fit the following model as the primary multivariable model that include only sites and clinic types for adjusting purpose.

$$\text{Logit}(P(\text{SVR})) = b_0 + b_1 * \text{TRT} + b_2 * \text{Site1} + \dots + b_8 * \text{Site7} + b_9 * \text{Clinic\_Type}$$

+ Unbalanced Covariates

We will report the adjusted odds-ratio (OR) with a 95% confidence interval (CI) for the estimate of the DOT vs. PN effect on SVR. We will also compute 95% CIs for the overall and arm-specific SVR rate using an exact (Clopper-Pearson) method to compare with results from other trials. Again, this analysis will be repeated for each of the three analytic samples albeit with different adjusting variables depending on the constituency of the samples: mITT, ITT and PP.

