### 5.5 Power analysis

The HERO study was planned to recruit N=300 participants in each arm in the mITT sample. Considering the base 80% SVR rate in the PN arm, a minimum difference of 9% between the two arms will be detected (i.e., 89% vs. 80%, OR=2.1) with the planned sample size in a multivariable logistic regression model in which adjusting variables explain 10% of variation in the predictor variable. This study posits that a >9% difference in SVR between the PN and DOT groups will be clinically significant based on studies that showed that SVR in treatment naive patients was >90%.

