### 8.3.3 Power analysis

We hypothesize that patients in the DOT arm will have higher treatment completion rate, compared to the PN arm, which is expected to have 80% completion rate. Like SVR rates, we will be able to detect a minimum of 9% difference in completion rates between the two arms (i.e., 89% vs. 80%, OR=2.1) with the planned mITT sample size of N=100 in each study arm.

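### Treatment initiation: the protocol (7 points) and the SAP (12 points) give different minimum detectable differences from the same inputs, and the correct figure is about 9

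*SAP*

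**What the plan says.** **Initiation.** In the protocol's section 11.10 power analysis, the mDOT arm is expected to have 60% initiation and "a minimum of 7% difference will be detectable (i.e., 60% vs. 67%, OR=0.74"), in a logistic model whose covariates explain 10% of the variation in the predictor. It adds: "Note that sample size for this analysis will be N=1000, the total number of randomized participants". Section 11.4 of the protocol fixes the operating characteristics: "The target power is 80% with a two-sided significance level of 0.05".

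SAP section 8.2.2 keeps the 60% rate and the 10% allowance but says: "With the planned N=1000 ITT sample size, we will be able to detect a minimum of 12% difference (i.e., 60% vs. 72%, OR=0.58"). SAP section 3.3 sets alpha: "a two-tailed significance level of 0.05 will be applied to all testing and confidence intervals". The SAP names no target power. Neither document explains the change from 7 to 12.

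**Related planning figures.**
- SAP 8.3.3 claims a 9-point detectable difference in completion "with the planned mITT sample size of N=100 in each study arm", whereas SAP 5.5 says "The HERO study was planned to recruit N=300 participants in each arm in the mITT sample".
- SAP 6.3 prints a minimum SVR difference of at least 157% for a 20% subgroup (N=120). For its own 20% subgroup (N=108), protocol 11.10 gives 17%.
- Protocol 11.11 equates an odds ratio of at least 1.8 for resistance with rates of 7% vs 14.4%.

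**The concern.** Two governing documents describe the same test on the same sample and give sensitivities five points apart. Each stated odds ratio agrees with its own pair of rates (60% vs 67% gives 0.739; 60% vs 72% gives 0.583), so neither figure is a single misprinted digit. Attrition cannot explain the gap. Both texts name N=1000, and SAP 8.1 defines initiation so that no randomised participant has an undetermined status.

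Initiation is the outcome on which PN is expected to do better, and the only one that the SAP confines to the ITT sample. If the comparison is null, readers will look to the planning figure to judge what could have been missed. The protocol's figure would tell them that a 7-point difference was likely to be found.

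**Working it through.** **Inputs.** Base rate 60% (protocol 11.10, SAP 8.2.2). 500 per arm (protocol 5.4, 1:1 allocation of 1000). R² = 0.10 (both power sections). Two-sided alpha 0.05 (protocol 11.4, SAP 3.3). Power 80% (protocol 11.4, assumed to carry over to the SAP).

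**Formula.** Two-proportion test with pooled variance under the null. The covariate allowance enters as n_eff = n(1 − R²) = 500 × 0.9 = 450 per arm. With d = p₂ − p₁ and p̄ = (p₁ + p₂)/2:

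z_power = [d√n_eff − 1.96 √(2p̄(1−p̄))] / √(p₁(1−p₁) + p₂(1−p₂))

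**Protocol figure, 60% vs 67%.** p̄ = 0.635, so the two root terms are 0.6808 and 0.6790. z = (0.07 × 21.213 − 1.96 × 0.6808)/0.6790 = (1.4849 − 1.3344)/0.6790 = 0.222. Power is 58.8% (63.3% with R² = 0).

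**SAP figure, 60% vs 72%.** p̄ = 0.66, so the root terms are 0.6699 and 0.6645. z = (0.12 × 21.213 − 1.96 × 0.6699)/0.6645 = (2.5456 − 1.3130)/0.6645 = 1.855. Power is 96.8%.

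**Solving for d at N=1000:**

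| Setting | Minimum detectable difference |
|---|---|
| 80% power, R² = 0.10 | 8.9 points (60% vs 68.9%, OR 0.68) |
| 80% power, R² = 0 | 8.5 points |
| 90% power, R² = 0.10 | 10.3 points |
| 80% power, R² = 0.10, continuity-corrected | 9.1 points |
| 80% power, one-sided 0.05, R² = 0 | 7.6 points |

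No variant gives 7 points, and neither 80% nor 90% power gives 12. At 60% vs 69% the power is 80.7%. A Wald test on the log odds ratio gives 58.6%, 80.4% and 96.6% for 67%, 69% and 72%.

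**Sample size needed for 80% power, R² = 0.10.** 7 points: 741.3/0.9 = 823.7, or 824 per arm. 12 points: 243.4/0.9 = 270.5, or 271 per arm. The second is almost exactly the attrition-reduced 270 per arm of protocol 11.4. That may be where the SAP's 12 points came from, but the documents do not say so.

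**Related figures.**
- *Completion, 80% vs 89%, R² = 0.10.* Power is 38.4% at 100 per arm and 82.6% at 300 per arm. The 9-point claim is sound at the planned 300, so only the printed N is wrong.
- *20% subgroup, base 80%, 80% power.* N=120 with R² = 0.10 gives 60 × 0.9 = 54 effective per arm and 17.0 points. N=108 without adjustment gives the same 54 per arm and 17.0 points. N=120 without adjustment gives 16.4 points.
- *Resistance.* OR for 14.4% vs 7% = (0.144/0.856)/(0.07/0.93) = 2.23. An OR of 1.8 from 7% corresponds to 11.9%. Assuming an even split (270 per group), power is 79.6% for 7% vs 14.4% and 49.9% for 7% vs 11.9%. The printed rates therefore fit the 80% target and the printed OR does not.

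**The case against.** The strongest reply is that the SAP half rests on an imported input. The 80% target appears only in the protocol, and at N=1000 a 12-point difference is detectable with ample power, so the SAP overclaims nothing. This stands in part. The SAP's fault is limited to calling 12 points the minimum, which is untrue at 80% or 90% power. The protocol's 7 points needs no such allowance, because it fails the protocol's own explicit target.

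A second reply is that little depends on either figure. Protocol 11.4 says the sample size was fixed by feasibility, initiation is secondary, and no decision rule uses these numbers. SAP 5.4 says "We will report the adjusted odds-ratio (OR) with a 95% confidence interval (CI"), and SAP 8.2.1 carries that approach over to initiation. The interval will show what the data exclude. All of this is correct and keeps the point minor.

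The related figures need hedging. The 157% may come from text extraction or merged digits rather than from the SAP itself, and should be checked against the source file. The protocol's 17% was worked for N=108, not N=120. The resistance powers assume an even split of the factor, which protocol 11.11 does not state, although the mismatch between the odds ratio and its rates does not depend on that assumption.

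**Conclusion.** The contradiction is real, and both initiation figures are wrong as minima. On the stated inputs the minimum detectable difference is 8.9 points at 80% power. The protocol is optimistic by about 2 points: a true 7-point difference would be missed about 41% of the time, not 20%. The SAP is conservative by about 3 points. This rests on 1:1 allocation of 1000, R² = 0.10 and 80% power for the SAP; dropping the R² adjustment moves the answer only to 8.5. If the 375 and 379 heading the columns of SAP Table 1 are the randomised totals (an assumption), the figure is 10.2 points.

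Severity is minor. No analysis, sample size or primary power changes. The completion N and the resistance odds ratio are labelling errors around sound calculations. The 157% is either the same or an artefact.

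**What to change.** State one initiation figure in protocol 11.10 and SAP 8.2.2: about 9 points (60% vs 69%, OR about 0.68) at N=1000, 80% power, two-sided 0.05 and R² = 0.10, and name the power in the SAP. If 754 is confirmed as the number randomised, a figure of about 10 points could be added, but this is optional.

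At the same time:
- in SAP 8.3.3, change N=100 to N=300 per arm;
- in SAP 6.3, check the 157% against the source file and, if it is there, replace it with 17% at N=120 and R² = 0.10;
- in protocol 11.11, change the resistance odds ratio from 1.8 to about 2.2 to agree with 7% vs 14.4%, and state the split assumed for the factor.

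The cost is text only. The protocol's initiation figure becomes less favourable (7 to 9 points) and the SAP's more favourable (12 to 9).

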### 8.3 Treatment Completion

The primary treatment completion outcome (100% completion) will be declared “yes” if a participant went through at least 84 days of treatment from his/her start treatment date to end treatment date regardless of adherence to the medications. By this definition, there will be no undetermined treatment completion status in any of the three analytic samples. The secondary treatment completion outcome (80% completion) will be determined based on whether a patient was treated for 68 days at least, which is 80% of the prescribed 84 treatment days, i.e., whether or not the length between the start and end dates (both inclusive) are greater than or equal to 68 days. The third treatment completion outcome will be the number of treatment days within the 84-day window on a continuous scale. Comparisons of median treatment days, third completion outcome, will be conducted as a secondary analysis.

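### Median treatment days capped at 84 will read 84 in both arms of the mITT sample at the planned completion rates, and the SAP names no test for this outcome

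*SAP*

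**What the plan says.** SAP 8.3 defines three completion outcomes. The primary one is binary: a participant completes if he or she "went through at least 84 days of treatment from his/her start treatment date to end treatment date regardless of adherence to the medications". The second is also binary, with a 68-day threshold. The third is "the number of treatment days within the 84-day window on a continuous scale", and the plan for it is one sentence: "Comparisons of median treatment days, third completion outcome, will be conducted as a secondary analysis". No test or effect measure is given.

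SAP 8.3.2 carries over the SVR procedures, which are logistic models for a binary outcome, and applies them to the ITT, mITT and PP samples. SAP 4.2 names t-tests or Mann-Whitney tests for continuous variables, but only for baseline characteristics.

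On rates, SAP 8.3.1 hypothesises higher completion in DOT, "compared to the PN arm, which is expected to have 80% completion rate" (SAP 8.3.3). The 89% for DOT is a detectable alternative rather than an expected rate. In the Protocol's words (section 11.10), "a minimum of 9% difference in completion rates between the two arms will be detectable (i.e., 89% (mDOT) vs. 80% (PN), OR=2.1".

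**The concern.** A median ignores everything that happens on the other side of the 50% point. Here the cap and the definition of completion coincide: a participant treated for 84 days or more scores 84, and only those who stop early score less. If most participants in both arms complete, the two medians are the same number however many stop early and whenever they stop.

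The analysis would then report 84 versus 84 days even if the effect on completion that the trial is sized for is present. Set beside the completion rates, that line adds nothing. Read alone, it could pass for evidence of equal treatment duration. Because no test is named, the two independent statisticians could also analyse this outcome differently.

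**Working it through.** **Inputs**
- Cap of 84 days; completion means at least 84 days from start to end date (SAP 8.3).
- PN completion 80% (expected); DOT 89% (minimum detectable).
- n per arm: 270 after attrition (Protocol 11.4) or 300 in mITT (SAP 5.5). SAP 8.3.3 prints 100, which conflicts with SAP 5.5. It does not affect the median result below.
- "The target power is 80% with a two-sided significance level of 0.05" (Protocol 11.4). Covariates explain 10% of the predictor's variation (stated for SVR, assumed here for completion).
- Initiation: DOT 60% expected; PN 67% (Protocol 11.10) or 72% (SAP 8.2.2), both being minimum detectable rates.
- Assumed, because the documents do not give it: the days on which non-completers stop, taken as the same in both arms.

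**The plan's own figure.** Power = Φ[(d√n − 1.96√(2p̄q̄)) / √(p₁q₁ + p₂q₂)], with d = 0.09, p̄ = 0.845 and n = 270 × 0.9 = 243. This is Φ[(1.403 − 1.003)/0.508] = 78.4%. The rate detectable with 80% power is 89.2% (OR 2.06), so the 9 points are reproduced. With n = 300 × 0.9 = 270, power is 82.6%.

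**mITT medians.** The sample median is 84 when more than half of the arm completes. At 80% and n = 300 the expected count is 240 with SD √(300 × 0.8 × 0.2) = 6.9, and the requirement is more than 150, which is 13 SD lower. The binomial probability is 1.000 at both 80% and 89%, for n = 100, 270 and 300. In simulation with 300 per arm at 80% versus 89%, the medians differed in 0 of 4,000 trials (stoppers uniform over days 1–83), and in 0 of 2,000 trials each for stoppers at days 60–83 and at days 1–30.

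**Information left in the same data**

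| Stopping days (assumed) | Mean difference | Rank test | t-test | Chi-square on completion |
|---|---|---|---|---|
| 60–83 | 0.09 × (84 − 71.5) = 1.1 days | 87% | 76% | 87% |
| 1–83 | 0.09 × (84 − 42) = 3.8 days | 87% | 75% | 87% |
| 1–30 | 0.09 × (84 − 15.5) = 6.2 days | 89% | 88% | 88% |

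The rank test follows the completion-rate test closely in every row, so its variation of a point or two between rows is mainly simulation error. At 270 per arm with stoppers uniform over 1–83, the rank test has 83% power.

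**ITT, non-initiators scored 0 (assumed).** Completion is 0.60 × 0.89 = 53.4% in DOT, and 0.67 × 0.80 = 53.6% or 0.72 × 0.80 = 57.6% in PN. At 500 per arm, the chance that half or fewer complete, so that the median is below 84, is:
- DOT at 53.4%: 7%
- PN at 53.6%: 6%
- PN at 57.6%: under 0.1%

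If DOT completion among initiators were also 80%, ITT completion would be 0.60 × 0.80 = 48% and the DOT median would fall below 84 in about 83% of trials.

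Initiation also dominates the ITT mean. With stoppers uniform over 1–83, DOT is 0.60 × (0.89 × 84 + 0.11 × 42) = 47.6 days. PN is 0.67 × (0.80 × 84 + 0.20 × 42) = 50.7 days, or 54.4 days at 72% initiation. The ITT difference then favours PN although DOT initiators stay on treatment longer.

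**The case against.** The strongest reply is that comparing medians is common shorthand for reporting medians beside a rank test, and that SAP 4.2 shows these authors use Mann-Whitney tests. On that reading the test works well. A reader might infer that the planned comparison cannot detect any difference, but the documents do not support that: they name no test, and a rank test on the capped data would have about 86–87% power. What remains is that SAP 4.2 covers baseline characteristics only, that the logistic models carried over by SAP 8.3.2 do not fit a count of days, and that the named summary would still read 84 versus 84 with no estimate of size.

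Two other stronger readings also fail. One is that the planning rates guarantee equal medians in the ITT sample too. They do not, because ITT completion is only just above half. The other is that 89% is the expected DOT rate. It is the smallest rate the trial could detect against 80%, though this changes nothing in mITT, where any rate above 50% gives a median of 84.

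It can also be said that treatment days might mean days with a dose taken, in which case the cap need not bind. SAP 8.3 measures completion by dates and regardless of adherence, and SAP 8.4 handles doses separately, so duration is the natural reading.

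Finally, this is the third version of a secondary outcome, and the two binary versions carry the completion hypothesis. That is correct and limits the consequence.

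**Conclusion.** The point holds for the medians in mITT, and in PP if completion there is similar or higher. At any completion rate above 50% in both arms, a difference in medians or a median regression is 0 regardless of the effect. That result does not depend on when stoppers stop or on the 89% figure. It rests on treatment days meaning start-to-end duration.

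The outcome itself is not uninformative. The hidden difference in means is about 1.1 to 6.2 days over the assumed stopping patterns (3.8 if uniform). In ITT the median sits close to a threshold, so whether it stays at 84 depends largely on initiation, and the SAP does not say how non-initiators are scored for this outcome. No primary conclusion is affected.

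**What to change.** In SAP 8.3, replace the median comparison with:
- **Estimate:** the between-arm difference in mean treatment days restricted to 84 days, with a bootstrap or robust 95% CI.
- **Test:** a rank-sum test stratified by the randomisation factors, with sparse cirrhosis strata handled as SAP 5.4 already foresees. State that this is the test and that the CI describes size, because a test of means is weaker under two of the three stopping patterns above.
- **Description:** medians may stay as description only.
- **ITT:** state how non-initiators are scored. If they are scored 0, say that the ITT result combines initiation with duration.

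The cost is a change of SAP wording. No new data are needed, and the binary completion outcomes are unchanged.
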